8.0 PRETREATMENT EVALUATION

No additional pretreatment evaluation will be necessary other than those required for the lung biopsy procedure as per standard of care. These include pre-procedure imaging and routine blood tests such as Prothrombin Time, INR, Platelet counts, WBC and pre-surgical testing if deemed necessary by the treating physician. Depending on the type of medications, non-steroidal anti inflammatory drugs, anti platelet agents and anticoagulants are held from 1-5 days from the date of biopsy.

9.0 TREATMENT/INTERVENTION PLAN

Both ABPI and the BioSentry are being used during routine lung biopsy procedures in MSKCC IR service although inconsistently, with preferences and usages varying among practitioners. Candidates enrolled in the study will selectively receive one or the other intervention as part of standard treatment protocol during lung biopsy procedures. Either one of these interventions is considered as an equivalent standard of care, and no additional fees should be incurred for the sole purpose of research.

Randomization will be done electronically after patient registration. Either the blood patch will be drawn or the BioSentry device will be made available at the start of the procedure in the IR room based on the randomization arm. If the patient was assigned to the ABPI group, a blood patch will be administered using the clotted blood in the labeled syringe obtained at the beginning of the procedure. The guiding needle will be retracted up to 2 cm from the pleural surface, and the blood will be injected slowly and steadily as the needle is pulled back out of the pleura.

If the patient is assigned to the BioSentry group, using the manufacturer's deployment system the introducer needle is positioned so that the tip is at least 1.5 cm deep to the visceral pleura. The coaxial introducer needle hub will be prehydrated with a drop of saline, and the tract plug housing will be mated and locked to the hub. The plug will be deployed.

10.0 EVALUATION DURING TREATMENT/INTERVENTION

After the biopsy, the patient will be transferred to the recovery unit. Two chest radiographs will be obtained immediately and 2 hours after the procedure as per standard of care. Additional radiographs may be obtained when indicated as per standard of care.

Patients with no or with a small stable asymptomatic pneumothorax on the post procedure chest radiographs will be discharged.

A chest tube will be placed for patients with a large pneumothorax, patients with a pneumothorax that is increasing in size rapidly, or symptomatic patients with any pneumothorax. Patients who undergo chest tube placement will generally be admitted for overnight observation. Chest tubes will be removed when there is no longer an air leak and the radiographic appearance remains stable for 2 hours with the chest tube clamped. This happens the next day of the biopsy for the majority of cases. Patients will be discharged home once the chest tube is removed. At the time of discharge all patients will be given contact information and will be asked to call back with any symptoms that might be related to delayed pneumothorax. In addition, patients who did not have a chest tube placed will be followed up with a phone call within two weeks for assessment of delayed pneumothorax, a rare occurrence. The only step in the peri, intra and post procedural management of these patients which is not a part of standard of care is the one-week post procedure phone call. All other steps are within standard of care. Any treatment as a consequence to the follow-up phone call is also a part of standard of care.

In case any of the study patients present with symptomatic or incidental delayed pneumothorax after being discharged, these patients will be captured for analysis.

To help keep impartiality, in addition to the standard of care review of post biopsy chest x-rays, at a later time, all chest radiographs will be reviewed by an interventional radiologist who was not involved with the biopsy procedure and is unaware of the randomization arm. All disagreements will be solved based on consensus after a third impartial interventional radiologist reviews the images.

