The post procedure chest radiographs will be evaluated by the biopsy operator for the presence of pneumothorax which will appear as free air collection overlying the lung parenchyma inside the chest wall. A Pneumothorax is generated from air leaking from the needle puncture site into the visceral pleura. Patients with no or small stable asymptomatic pneumothoraces will be discharged.

A chest tube will be placed for patients with a large pneumothorax, patients with a pneumothorax that is increasing in size, or symptomatic patients with potentially any size pneumothorax on post procedure chest radiographs. Most patients who undergo chest tube placement will be admitted for overnight observation. Chest tubes will be removed when there is no longer an air leak and the radiographic appearance remains stable for 2 hours

with the chest tube clamped. This happens the next day of the biopsy for the majority of cases. Patients will be discharged home once the chest tube is removed. At the time of discharge all patients will be given contact information and will be asked to call back with any symptoms that might be related to delayed pneumothorax. In addition, patients who do not have a chest tube placed will be also followed up with a phone call by a member of IR service at one week checking for delayed pneumothorax (appendix 20.4). In case any of the study patients present with symptomatic or incidental delayed pneumothorax after being discharged, these patients' data will be captured for analysis. This phone call is the only part of this study which is not a part of standard of care however any consequent interventions based on the phone call are within standard of care practice.

All biopsy chest radiographs and CT images will be analyzed by the radiologist performing the procedure to identify emphysema (appendix 20.2.2) if present. The prescan images, as well as any recent chest CT studies, if available, will be examined in lung windows on the PACS workstation. The lung parenchyma surrounding the lesion and in the region of the biopsy needle course will be analyzed for emphysema, blebs and transfissural approach.

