12.0 CRITERIA FOR THERAPEUTIC RESPONSE/OUTCOME ASSESSMENT

Lack of any detectable pneumothorax as visualized on post procedure chest radiographs at 2 hours following the procedure is considered success. The rate of any pneumothorax that did not require treatment as well as those which require chest tube placement will be captured for analysis in each group.

Lack of prospective follow up chest x-ray at one week after biopsy will lower the accuracy of the study due to suboptimal capturing of delayed pneumothoraces by a phone call although this number is expected to be very low. For patients that are unable to be reached or unable to complete the follow up phone call, the incidence of a delayed pneumothorax and/or chest tube placement will be determined by a review of the patient's chart by the PI in the 2 weeks following the lung biopsy.

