20.4 PHYSICIAN DATA FORM

Effect of Autologous Blood Patch Injection versus BioSentry hydrogel Tract Plug in the reduction of pneumothorax risk following lung biopsy procedures

1- Patient Demographics

MRN		Procedure date		/	/	
Last Name		Male	Female	DOB	/	/

2- Candidate for study Yes No

If no, please explain why or list/circle exclusion criteria #:

3- Consent obtained Yes No

4- Randomization # _____

5- Procedure parameters

Exclusion criteria

1. Passage through non-aerated lung or tissue OR Target lesion located LESS than 1.5 cm away from visceral pleura
2. Needle path transgressing pleural fissure or bleb
3. Coaxial technique not needed
4. Needle size 17 gauge
5. Prior ipsilateral lung interventions: biopsy, chest tube, surgery, radiation or pleurodesis

Target size (largest transverse diameter on reference image) _____ cm

Target depth (Needle path distance from pleura to outer edge of target) _____ cm

Lobe (please circle) RUL RML RLL LUL LLL

Position (please circle) Prone Other:

Type of biopsy (please circle) FNA Core Both

Number of biopsy samples FNA: Core:

6- Factors affecting outcome: Did you encounter (please circle)

More than 1 pleural puncture? Yes No

Passage through a fissure? Yes No

Complete passage through non aerated lung? Yes No

Passage through a bleb/bulla? Yes No

Usage of BARE needle WITHOUT coaxial system? Yes No

Intraprocedural pneumothorax? Yes No

Significant needle path hemorrhage within 2 cm of pleura? Yes No

7- Sealant technique used (please circle) Blood patch BioSentry None
 (Please note reason below)

8- Outcomes

Pneumothorax on CXR (please circle) Yes No

Pneumothorax - Second reader (please circle) Yes No

Chest tube placement (please circle) Yes No

Delayed complications (please circle) Yes No If Yes: _____

Notes:

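### Disputed chest films are settled by a consensus that is not confined to masked readers, which leaves room for knowledge of the arm to affect the primary endpoint

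*Combined protocol and SAP*

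**What the plan says.** Section 4.3 gives the first read to the person who did the biopsy: "The post procedure chest radiographs will be evaluated by the biopsy operator for the presence of pneumothorax". That person has just placed the sealant and cannot be masked.

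Section 10.0 adds a later safeguard, introduced as a means of keeping the assessment impartial: "all chest radiographs will be reviewed by an interventional radiologist who was not involved with the biopsy procedure and is unaware of the randomization arm". The next sentence deals with conflicts between the reads: "All disagreements will be solved based on consensus after a third impartial interventional radiologist reviews the images".

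Section 4.3 counts any pneumothorax that can be discerned on a chest film as an event. It also counts a CT finding that is more than minuscule. Section 14.0 takes the primary endpoint from CT or chest films within 2 hours and does not mention the masked review or say which read enters the analysis. The physician data form (20.4) has one field for the chest film result and one for the masked read, "Pneumothorax - Second reader (please circle) Yes No", but none for a third read or a final adjudicated result.

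**The concern.** The masked review protects the endpoint where the operator and the second reader agree. Where they disagree, one party is always the unmasked operator, and the case goes to a consensus whose members and decision rule are not given. The third read comes before the consensus and is not itself the decision. Two safeguards are spelled out for the second reader (uninvolved, and unaware of the arm). The third reader is described only as impartial.

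Because the threshold is any discernible air on a film, disputes will tend to concern small findings, where judgement matters most. The trial is a non-inferiority comparison with a 10-point margin, and Section 3.0 says the purpose is to justify using ABPI exclusively. A tilt in disputed reads toward ABPI would raise the chance of a false non-inferiority claim. A tilt the other way would cost power.

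**Working it through.** **Inputs from Section 14.0:** 276 patients per arm; margin 10 points; BioSentry rate 20%; one-sided alpha 5%; power 90%; bounds Z = -2.538 at half information and Z = -1.662 at the end. Equal true rates of 20% for the power calculation are an assumption; the plan does not state the ABPI rate, but this value reproduces its sample size.

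**Reproducing the plan's figures**

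- Fixed-design size: n = (1.645 + 1.282)² × (0.2×0.8 + 0.2×0.8) / 0.10² = 8.564 × 0.32 / 0.01 = 274.04, so 275 per arm before allowing for the interim look.
- Two looks, as a bivariate normal with correlation √0.5 and the stated bounds: overall one-sided alpha is 0.0500, and power at 276 per arm is 0.9000.

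The design figures therefore hold, and the adjudication rule does not affect them.

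**Adding a reading tilt**

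Let b be the net shift in the observed ABPI rate caused by how disputed films are settled. The documents give no disagreement rate and no basis for b, so it is assumed. With p the observed ABPI rate:

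- SE = √[p(1-p)/276 + 0.2×0.8/276]
- drift at full information = [0.10 - (p - 0.20)] / SE

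The probability of declaring non-inferiority is the chance of crossing either bound with that drift (multiplied by √0.5 at the interim).

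| Situation | p | SE | Drift | Probability of declaring non-inferiority |
|---|---|---|---|---|
| True 30% v 20%, no tilt | 0.30 | 0.0366 | 0 | 5.0% |
| True 30% v 20%, 1 point toward ABPI | 0.29 | 0.0364 | 0.275 | 8.5% |
| True 30% v 20%, 2 points toward ABPI | 0.28 | 0.0362 | 0.553 | 13.7% |
| True 20% v 20%, no tilt | 0.20 | 0.0341 | 2.937 | 90.0% |
| True 20% v 20%, 1 point against ABPI | 0.21 | 0.0344 | 2.619 | 83.3% |
| True 20% v 20%, 2 points against ABPI | 0.22 | 0.0347 | 2.308 | 74.3% |

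A simpler check at the final look alone gives similar results: Φ(-1.662 + b/0.0366) is 4.8% with no tilt, 8.2% at 1 point and 13.2% at 2 points.

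**What a tilt of this size means in films**

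One point is 0.01 × 276 = 2.8, about 3 ABPI patients; two points is about 6. If 5% to 10% of films in that arm were disputed and a net 10% to 20% of those were tipped the same way, b would lie between 0.05 × 0.10 = 0.5 points and 0.10 × 0.20 = 2 points. Both ranges are assumptions.

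**The case against.** The strongest reply is that the text never says the operator joins the consensus. The paragraph sets out to secure impartiality and describes an uninvolved, masked second reader. The word impartial in the following sentence may be meant to carry both properties over to the third. Even if the operator took part, a true consensus would need the masked reader to agree, so the operator could not simply overrule. A masked reader sees every film, so any influence is confined to disagreements. All of this is fair. It limits the point to a rule that permits unmasked influence by silence; it does not supply the missing exclusion or the third reader's masking.

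A reader might infer from the stated aim that any bias would favour ABPI. The documents do not support that. Section 9.0 says practitioners' preferences vary, and Section 4.3 lets any attending, or a supervised fellow, do the biopsy. Tilts could cancel or run against ABPI.

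A reader might also infer that late outcomes are settled by an unmasked principal investigator, because they "will be determined by a review of the patient's chart by the PI". The documents do not say whether that person is masked. The review is a fallback: "For patients that are unable to be reached or unable to complete the follow up phone call". It bears only on secondary outcomes, and Section 1.0 expects delayed pneumothorax in under 1% of patients. It is not part of this point.

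Finally, the absence of a field on the physician's form does not show that the adjudicated result goes unrecorded, since Section 16.1 provides for a separate secure database.

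**Conclusion.** The point holds as a weakness in the adjudication rule, not as a demonstrated bias. Section 10.0 provides a masked read of every film, then sends the films on which masking matters most to a process that is not limited to masked readers. In this design a net change in about 3 to 6 ABPI patients would matter, as the table shows in both directions. Those figures depend wholly on an assumed tilt and show how sensitive the design is; they do not estimate what this clause would cause.

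A related gap belongs with it: the masked review covers chest radiographs only, although CT findings above the minuscule threshold also count as events. No masked CT read is specified.

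**What to change.** In Section 10.0, replace the consensus rule with wording such as: *disputed films are decided by the third radiologist's independent read, made unaware of the arm and of the first two reads; the operator takes no part*. State there and in Section 14.0 that, for disputed films, this result is the radiograph component of the primary endpoint, and record it in the trial data. State also how CT findings that count as positive combine with the radiograph result, given that the masked review does not now cover CT.

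The cost is small. The second and third readers are already planned, the sample size does not change, and the operator's real-time read for patient care is unaffected. The one downside is that the operator cannot explain an ambiguous film to the adjudicator.

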11.0 TOXICITIES/SIDE EFFECTS

There are no anticipated additional side effects to the intervention other than those expected during regular lung biopsy procedures.

12.0 CRITERIA FOR THERAPEUTIC RESPONSE/OUTCOME ASSESSMENT

Lack of any detectable pneumothorax as visualized on post procedure chest radiographs at 2 hours following the procedure is considered success. The rate of any pneumothorax that did not require treatment as well as those which require chest tube placement will be captured for analysis in each group.

Lack of prospective follow up chest x-ray at one week after biopsy will lower the accuracy of the study due to suboptimal capturing of delayed pneumothoraces by a phone call although this number is expected to be very low. For patients that are unable to be reached or unable to complete the follow up phone call, the incidence of a delayed pneumothorax and/or chest tube placement will be determined by a review of the patient's chart by the PI in the 2 weeks following the lung biopsy.

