Pneumothorax (appendix 20.2.1) will be mainly defined based on post procedure chest x-rays. Any discernible pneumothorax on chest x-rays is considered a positive finding. Minuscule pneumothorax (a tiny film of air) which is sometimes seen on the last set of CT images of a biopsy procedure after the introducer needle is removed is not considered a positive finding. This is due to high sensitivity of CT imaging. Any pneumothorax larger than minuscule on CT images is considered a positive finding.

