14.0 BIOSTATISTICS

This is a randomized trial comparing autologous blood patch injection with BioSentry on the rate of pneumothorax after percutaneous lung biopsy. The primary endpoint is the rate of pneumothorax within 2 hours following biopsy. Pneumothorax is observed on post procedure CT scan or on follow-up chest radiographs while the patient is in the recovery room, according to standard of care.

This study will have a non-inferiority design to evaluate whether ABPI is associated with less than a 10% increase in pneumothorax rate compared to BioSentry. We will test the null hypothesis that ABPI is inferior, with a 10% or more increase in pneumothorax rate compared to BioSentry. The non-inferiority margin of 10% is considered clinically acceptable. Allowing for 1 interim assessment, the study will require 276 patients in each arm (552 patients total) to have 90% power to test this hypothesis. This sample size estimate assumes the pneumothorax rate with tract plug is approximately 20% based on a randomized study by Zaetta et al. An interim assessment will be performed after approximately half the patients (roughly 276 patients) have been enrolled onto the study. Using the Lan-DeMets spending function, the trial will terminate early for non-inferiority if with half the patients, a one-sided nominal Z-score of -2.538 ($p\text{-value} \leq 0.0056$) is observed. This nominal z-score will be recalculated based on the available exact information fraction at the time of the Data Safety Monitoring Board review. If the trial continues, the final assessment will use a Z-score of -1.662 with an associated $p\text{-value}$ of 0.0482. This preserves a 5% overall probability (1-sided type I error) of falsely concluding that ABPI is non-inferior to tract plug when it is truly worse. In 2012 IR service performed 1128 lung biopsies. IR service currently performs around 100 lung biopsies each month. With an anticipated eligibility rate of 50%, this study will take up to 24 months.

All randomized patients who undergo a biopsy will be analyzed for the primary outcome on a modified intent-to-treat basis according to the randomized treatment assignment regardless of the actual intervention received. The difference between pneumothorax rates for ABPI and BioSentry will be estimated and assessed using a Z-test. The same analysis method will be used to perform a secondary analysis on only patients who have a sealant placed after their biopsy.

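### The primary endpoint is scored inconsistently for a pneumothorax seen on CT but not on chest radiographs, and the plan neither records CT findings as an outcome nor has them read blind

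*Combined protocol and SAP*

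**What the plan says.** All references are to the combined protocol and SAP.

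- **Section 12.0** (outcome assessment): "Lack of any detectable pneumothorax as visualized on post procedure chest radiographs at 2 hours following the procedure is considered success". CT is not mentioned.
- **Section 20.3.1** (appendix definition): the diagnosis is made on the chest radiograph. CT is not mentioned.
- **Section 4.3**: pneumothorax is defined *mainly* on post-procedure chest x-rays, where any discernible finding is positive. A minuscule CT finding does not count, but "Any pneumothorax larger than minuscule on CT images is considered a positive finding". The exempted category is described as "Minuscule pneumothorax (a tiny film of air) which is sometimes seen on the last set of CT images of a biopsy procedure" after the introducer has been removed.
- **Section 14.0** (biostatistics): the primary endpoint is the pneumothorax rate within 2 hours, and "Pneumothorax is observed on post procedure CT scan or on follow-up chest radiographs while the patient is in the recovery room". No CT size threshold is given.

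On who reads what:

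- **Section 4.3**: "The post procedure chest radiographs will be evaluated by the biopsy operator for the presence of pneumothorax". On CT, "All biopsy chest radiographs and CT images will be analyzed by the radiologist performing the procedure to identify emphysema"; the same paragraph extends the look to blebs and a transfissural approach.
- **Section 10.0**: to keep impartiality, "all chest radiographs will be reviewed by an interventional radiologist who was not involved with the biopsy procedure" and does not know the arm. A third reader helps settle disagreements.
- **Section 20.4** (data form), Outcomes block: "Pneumothorax on CXR (please circle) Yes No", followed by a second-reader item with no modality. There is no CT outcome item.

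**The concern.** This is a non-inferiority trial with a binary primary endpoint, so one rule must decide who is an event. Here two stated rules disagree about a patient whose pneumothorax shows on CT but on no radiograph. Section 4.3 says that minuscule air is sometimes seen on the last CT images and gives a separate rule for anything larger, so the authors expected CT findings to arise.

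The weakness is compounded by ascertainment. The plan sets up a blinded second read for radiographs, but a CT-only event would rest on the radiologist who delivered the sealant. The boundary between minuscule and larger is a verbal description without a measurement, and the form has no outcome field for the result. If this is left open, the choice between a radiograph-only endpoint and a radiograph-or-CT endpoint could be made after results by arm are known.

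**Working it through.** **1. Classify the patients under each section.**

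| Patient | 4.3 | 14.0 | 12.0 and 20.3.1 |
|---|---|---|---|
| Pneumothorax on the 2-hour radiograph | event | event | event |
| Larger-than-minuscule air on post-procedure CT, all films clear | event | event | **not an event** |
| Minuscule air on final CT, all films clear | not an event | no threshold stated; not an event if 4.3 is read in | not an event |

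The second row is the direct contradiction. The third row is not one, provided that 14.0 is read with 4.3.

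**2. Check whether the data would allow repair.** The nearest form item is the yes/no question on intraprocedural pneumothorax. It is listed among factors affecting outcome, not among outcomes. It gives no size, no modality and no timing relative to the sealant, so it cannot separate air that arose before deployment from air on the final CT. The second-reader item names no modality, but Section 10.0 limits that read to radiographs.

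**3. Reproduce the plan's sample size.** Inputs from Section 14.0: 20% in both arms, margin 0.10, one-sided 5%, 90% power, 276 per arm, Z bounds −2.538 (interim) and −1.662 (final).

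Fixed design: n = (1.645 + 1.2816)² × 2 × 0.20 × 0.80 / 0.10² = 274.1, so 275 per arm. With both looks, 276 per arm gives 90.0% power and an overall one-sided error of 0.0500. The plan's figure stands and is not in dispute.

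**4. Illustrate sensitivity to uncounted events.** The sizes are assumed; the documents give no share of CT-only findings. Suppose that the 4.3 rule is the intended endpoint and the true rates lie on the null boundary, 30% ABPI v 20% BioSentry. The test declares non-inferiority when

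Z = (pA − pB − 0.10) / √[pA(1−pA)/276 + pB(1−pB)/276] ≤ −1.662.

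One percentage point is 276 × 0.01 = 2.8, or about 3 patients. At 29% v 20% the standard error is √[(0.29×0.71 + 0.20×0.80)/276] = 0.0364. The shift is 0.01/0.0364 = 0.275 standard errors, and the normal approximation gives Φ(−1.662 + 0.275) = 8.3%. Exact binomial sums at the final look give:

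| Recorded rates, ABPI v BioSentry | Meaning | P(declare non-inferiority) |
|---|---|---|
| 30% v 20% | nothing uncounted | 4.9% |
| 29% v 20% | one point lost, ABPI only | 8.4% |
| 30% v 19% | one point lost, BioSentry only | 2.7% |
| 29% v 19% | one point lost in both arms | 4.9% |

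Allowing for both looks changes these to 5.1%, 8.6%, 2.8% and 5.1%.

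**5. Effect of the definition on power.** If counting CT raised both arms equally from 20% to 22% or 25% (assumed), exact power at the final look would go from 90.0% to 88.1% or 85.4%.

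**The case against.** Section 4.3 makes radiographs the main basis for the diagnosis, so CT is supplementary and the affected patients may be few. That bears on size and stands. It does not remove the conflict, because the same paragraph counts the larger CT finding outright and 12.0 leaves it out.

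A reader might infer a three-way split in which 14.0, having no threshold, also counts a tiny film of air. The documents do not support that. Section 4.3 excludes minuscule findings expressly, while the sentence in 14.0 describes where pneumothorax is seen, much as the background in 3.0 does. A specific rule can be read into a general description. The omission in 14.0 is worth tidying, but it is not a rival definition.

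A reader might also infer that nobody looks at CT except for emphysema, or that the form holds nothing relevant. Both go too far. The operator also looks for blebs and a transfissural path, and the form does ask about intraprocedural pneumothorax. Neither supplies a blinded, sized CT outcome.

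Finally, the error-rate figures depend wholly on assumption: the opposite assumption reverses the direction, and equal loss changes nothing. If radiographs alone are the intended endpoint, uncounted CT findings cause no false non-inferiority at all. This is correct, and it limits what may be claimed.

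**Conclusion.** The point holds as an inconsistency in the primary endpoint. Sections 12.0 and 20.3.1 use radiographs only, 4.3 and 14.0 admit CT, and a CT-only pneumothorax larger than minuscule changes status accordingly. Its ascertainment is unblinded as far as the plan states, and it is not recorded as an outcome. It should be fixed.

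The effect is unknown. A reader might take the 8.4% as evidence that the trial's type I error is inflated. It is not: it needs a loss of one point confined to the ABPI arm, with the 4.3 rule as the true endpoint, and the documents give neither a count nor a direction. The figures show only that a difference of about 3 patients between arms would matter at the boundary.

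A minor related point: 12.0 refers to radiographs *at* 2 hours, while 2.1 and 14.0 say *within* 2 hours. Read literally, air on the immediate film that has gone by the later film is scored differently. This is probably loose wording, but the sections should agree.

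**What to change.** State one primary endpoint definition in 4.3, 12.0, 14.0 and 20.3.1, before any comparison by arm, and align the time window in 12.0 with 2.1 and 14.0. There are two coherent choices.

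**If the 4.3 rule is kept:**
- An event is any pneumothorax on a chest radiograph from needle removal through the 2-hour film, or any pneumothorax larger than minuscule on CT images.
- Say whether a pneumothorax seen on CT before sealant deployment counts. The wording of 4.3 is not limited to images after needle removal, and the same section keeps these patients in the primary analysis.
- Give *minuscule* an operational reading rule, and carry the threshold into 14.0.
- Add the relevant CT images to the blinded re-read and adjudication in Section 10.0.
- Add a CT outcome field to the form: none, minuscule or larger, and before or after sealant.

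**If radiographs alone are intended:** delete CT from the endpoint wording in 4.3 and 14.0.

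The first choice costs protocol wording, a form field and slightly more work for the existing blinded reader; it needs no new patients, imaging or reader. Blinding on CT may be imperfect if a sealant is visible, which the documents do not address, and the event rate may differ slightly from the assumed 20%. The second choice costs wording only. Either way, the change concerns endpoint scoring, not treatment.
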